7.2.9 Annual Follow-up Visit

After implant, scheduled follow-up visits are to be performed annually (± 60 days) from the implant date in order to capture:

- Spontaneous episodes that have not been previously reported;
- Adverse events that have not been previously reported;
- Programming changes that have not been previously reported;
- Product experience reports that have not been previously reported.

For participants in the S-ICD Clinical Investigation (IDE G090013), annual follow-up visit windows are calculated from the original S-ICD System implant date (day 0) and take into account the last follow-up visit conducted in the S-ICD Clinical Investigation (e.g., if the last follow-up conducted in the S-ICD Clinical Investigation (IDE G090013) was the 540 day follow-up visit, then the first S-ICD PAS annual follow-up visit should occur at 720 days post implant).

Aside from the annual follow-up visit, other scheduled and unscheduled visits throughout the year (e.g., standard of care device checks) should not be submitted unless they are associated with a Type I-II clinical event, device episode, suspected device malfunction or device programming change¹⁷, in which case they should be submitted as additional follow-up visits as described in Section 7.2.10, below.

The final annual follow-up visit must occur more than 1800 days after the initial implant procedure. The first standard of care visit within the annual follow-up visit window that occurs after the 1800 day mark should be submitted as an annual follow-up visit; if that is not possible, then the next standard of care visit may be submitted as an additional follow-up visit to allow for timely study completion. **Table 7** lists all the data required at annual follow-up visits.

¹⁷ A programming change refers to any difference between *Initial Device Settings* and *Current Device Settings* under the *Programmable Parameters* section of an S-ICD Summary Report.

Table 7: Annual Follow-Up Visit Data Collection

Data Collection	Retention of Original Source Documentation
Adverse events, if applicable	Investigational Center
Q-TECH Programmer Printouts: - Initial and Final Summary Reports - Captured S-ECG in each sensing vector - Device episodes, if applicable Shocked induced VT/VF episodes (external ECG strips), ¹⁸ if performed Chest x-ray(s) if applicable ¹⁹	Investigational Center; upload copy to Cameron Health/BSC
SD Card Data	Cameron Health/BSC (e.g. via CAMELION)

7.2.10 Additional Follow-up Visits

Physician office visits, emergency room visits, out-patient hospital visits, and hospitalizations related to the S-ICD System (associated with a Type I-II adverse event, treated episode, suspected device malfunction or device programming changes²⁰) should be recorded as an additional follow-up visit. A subject status check may also be performed by telephone and recorded as an additional follow-up visit under special circumstances defined by the sponsor or in order for the subject to complete the study after 1800 days post implant; otherwise, additional follow-up visits should not be reported unless they are associated with a Type I-II adverse event, treated episode, suspected device malfunction or device programming changes. **Table 8** lists all the data required from additional follow-up visits.

¹⁸ Induction testing is not required per protocol; upload only if performed. Any time induction testing is performed in the study, external ECG strips are only required for sustained ventricular arrhythmias that result in a shock, either from the S-ICD System or from an external defibrillator.

¹⁹ An X-ray is not required per protocol; upload only if a chest x-ray of the S-ICD System was taken to assess the position of the S-ICD System, an S-ICD System-related adverse event, or suspected product issue.

²⁰ A programming change refers to any difference between *Initial Device Settings* and *Current Device Settings* under the *Programmable Parameters* section of an S-ICD Summary Report.

Table 8. Additional Follow-Up Visit Data Collection

Data Collection	Retention of Original Source Documentation
Adverse events, if applicable	Investigational Center
Q-TECH Programmer Printouts: - Initial and Final Summary Reports - Captured S-ECG in each sensing vector, if sensing vector changed - Device episodes, if applicable Shocked induced VT/VF episodes (external ECG strips), ²¹ if performed Chest x-ray(s) if applicable ²²	Investigational Center; upload copy to Cameron Health/BSC
SD Card Data (if new spontaneous episodes were recorded)	Cameron Health/BSC (e.g. via CAMELION)

²¹ Induction testing is not required per protocol; upload only if performed. Any time induction testing is performed in the study, external ECG strips are only required for sustained ventricular arrhythmias that result in a shock, either from the S-ICD System or from an external defibrillator.

²² An X-ray is not required per protocol; upload only if a chest x-ray of the S-ICD System was taken to assess the position of the S-ICD System, an S-ICD System-related adverse event, or suspected product issue.

7.3 Revisions, Replacements and Explants

In the event that the electrode or PG is surgically revised after the initial implant procedure, the system revision form is used to record changes to the system. If either the PG or electrode is removed from service, a device status form must be completed for the out-of-service device(s). If the system is revised without replacing any system components, a system revision form is completed. If the PG or electrode is replaced, the new device(s) will be recorded on an additional implant form. **Table 9** lists all the data required for system revisions.

Table 9. System Revision Data Collection

Data Collection	Retention of Original Source Documentation
Adverse events, if applicable Newly implanted product and accessories utilized for S-ICD System (model/serial/lot/batch/etc.), if applicable	Investigational Center
Q-TECH Programmer Printouts: - Initial and Final Summary Reports - Captured S-ECG in each sensing vector, if sensing vector changed - Device episodes, if applicable Shocked induced VT/VF episodes (external ECG strips), ²³ if performed Chest x-ray(s) if applicable ²⁴	Investigational Center; upload copy to Cameron Health/BSC
SD Card Data (if new spontaneous episodes were recorded)	Cameron Health/BSC (e.g. via CAMELION)

²³ Induction testing is not required per protocol; upload only if performed. Any time induction testing is performed in the study, external ECG strips are only required for sustained ventricular arrhythmias that result in a shock, either from the S-ICD System or from an external defibrillator.

²⁴ An X-ray is not required per protocol; upload only if a chest x-ray of the S-ICD System was taken to assess the position of the S-ICD System, an S-ICD System-related adverse event, or suspected product issue.

7.4 Study Completion

Subjects may be withdrawn from the study for a variety of reasons including:

- Subject withdraws consent for any reason;
- Subject is lost to follow-up despite best efforts to locate the subject;
- The S-ICD System is permanently explanted;
- The subject has been followed >60 months from the original implant date.

Subjects who undergo a permanent explant or who commence, but do not complete, an implant procedure should be contacted, either in person or by telephone, at least 30 days after the permanent explant or implant attempt in order to record any adverse events before being withdrawn from the study. The study completion form documents withdrawal of any subject from the study.

There are no additional follow-up requirements once a subject has been withdrawn from the study. **Table 10** lists all the data that are required for study completion.

Table 10. Study Completion Data Collection

Data Collection	Retention of Original Source Documentation
Adverse events, if applicable	Investigational Center
Q-TECH Programmer Printouts: - Initial and Final Summary Reports - Captured S-ECG in each sensing vector, if sensing vector changed - Device episodes, if applicable Shocked induced VT/VF episodes (external ECG strips), ²⁵ if performed Death letter, if applicable Chest x-ray(s) if applicable ²⁶	Investigational Center; upload copy to Cameron Health/BSC
SD Card Data (if new spontaneous episodes were recorded)	Cameron Health/BSC (e.g. via CAMELION)

²⁵ Induction testing is not required per protocol; upload only if performed. Any time induction testing is performed in the study, external ECG strips are only required for sustained ventricular arrhythmias that result in a shock, either from the S-ICD System or from an external defibrillator.

²⁶ An X-ray is not required per protocol; upload only if a chest x-ray of the S-ICD System was taken to assess the position of the S-ICD System, an S-ICD System-related adverse event, or suspected product issue.

7.5 Adverse events and Spontaneous Episode Classification

Complications and treated spontaneous episodes will be preliminarily classified by investigational sites and reviewed for final adjudication by a Clinical Events Committee (CEC).

8. SUBJECT SELECTION

Subjects with a remaining life expectancy of at least 360 days who are eligible for implantation with an S-ICD System, OR who were previously implanted with an S-ICD System in the S-ICD System Clinical Investigation (IDE G090013) study, are eligible for participation. Approximately 1,616 subjects will be enrolled at a maximum of 150 investigational sites.

8.1 Subject Population

Any subject who meets the inclusion criteria, does not meet the exclusion criterion, and provides informed consent will be enrolled in the study upon undergoing an implant procedure for the S-ICD System. Subjects who do not undergo an implant procedure will not count toward the enrollment ceiling.

8.2 Devices Under Surveillance

The following information is a brief summary of the S-ICD System and its principle of operation. Refer to the S-ICD System User's Manuals for additional information.

8.2.1 SQ-RX Pulse Generator

The SQ-RX pulse generator comprises an inner structure of discrete electrical components, [REDACTED]

[REDACTED] The header contains a single port for connection of the Q-TRAK subcutaneous electrode to accommodate sensing, pacing, and defibrillation. [REDACTED]

[REDACTED] The SQ-RX pulse generator is capable of delivering high energy defibrillation shocks as well as bradycardia demand mode cardiac pacing for a period up to thirty seconds following defibrillation therapy. Future generations of the SQ-RX pulse generator may be included in the study.

8.2.2 Q-TRAK Subcutaneous Electrode

A horizontal bar chart with 15 black bars of varying lengths. The bars are arranged vertically, with the longest bar at the top and the shortest at the bottom. The chart represents the percentage of respondents for each statement. The statements are: "will be more..."; "will be less..."; "will be the same"; "will be more..."; "will be less..."; "will be the same"; "will be more..."; "will be less..."; "will be the same"; "will be more..."; "will be less..."; "will be the same"; "will be more..."; "will be less..."; "will be the same"; "will be more...".

Statement	Percentage
will be more... (top bar)	100%
will be less... (2nd bar)	~95%
will be the same (3rd bar)	100%
will be more... (4th bar)	100%
will be less... (5th bar)	~95%
will be the same (6th bar)	100%
will be more... (7th bar)	100%
will be less... (8th bar)	~95%
will be the same (9th bar)	100%
will be more... (10th bar)	100%
will be less... (11th bar)	~95%
will be the same (12th bar)	100%
will be more... (13th bar)	100%
will be less... (14th bar)	~95%
will be the same (15th bar)	100%

Future generations of the Q-TRAK subcutaneous electrode may be included in the study.

[figure not shown]
8.2.3 Q-GUIDE Electrode Insertion Tool

Term	Percentage
GMOs	~95%
Organic	~95%
Natural	~95%
Artificial	~85%
Organic	~85%
Natural	~85%
Artificial	~85%
Organic	~85%
Natural	~85%
Artificial	~85%

Future generations of the Q-GUIDE EIT may be included in the study.

8.2.4 Q-TECH Programmer Description

The Q-TECH programmer is a completely self-contained, non-sterile, non-implantable, lightweight, easily portable computer that does not allow general purpose computing. ■

Future generations of the Q-TECH programmer may be included in the study.

8.3 Study Inclusion/Exclusion Criteria

8.3.1 Inclusion Criteria

Subjects must meet the following criteria to be eligible for inclusion in the study:

- Eligible for implantation with an S-ICD System, OR previously implanted with an S-ICD System in the S-ICD System Clinical Investigation (IDE G090013)
- Willing and able to provide written informed consent or have informed consent as provided by a legal representative

8.3.2 Exclusion Criterion

Subjects who meet the following criterion must be excluded from the study:

- Remaining life expectancy of less than 360 days

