9. SUBJECT ACCOUNTABILITY

9.1 Point of Enrollment

A participant in the S-ICD Clinical Investigation (IDE G090013) who is implanted with the S-ICD System is considered enrolled upon signing the informed consent form (ICF). Subjects who did not participate in the S-ICD Clinical Investigation (IDE G090013) will be considered enrolled after both signing an informed consent and undergoing an implant procedure. A subject who signs an informed consent, but does not undergo an implant procedure does not count toward the enrollment ceiling and has no follow-up requirements.

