10. STATISTICAL CONSIDERATIONS

[figure not shown]
The S-ICD Post Approval Study is designed to examine the long-term safety and effectiveness of the S-ICD System. The study design includes two co-primary endpoints maintaining a family-wise significance level of 0.05 by defining a hierarchical testing procedure. The safety endpoint will be tested first. If the test is successful then the effectiveness endpoint will be tested at the same significance level. Primary endpoints will be tested prior to testing the secondary endpoints. Individual rates of each adverse event contributing to the primary safety endpoint will be examined including two-sided 95% exact confidence intervals. Other pre-specified observational analyses are defined to further investigate the long-term safety and effectiveness of the S-ICD System.

Subjects from the IDE study who provide informed consent for this study will be followed through 60 months post implant. All subjects enrolled in the S-ICD System Clinical Investigation (IDE G090013) who underwent an implant attempt will contribute to the analyses of the safety and effectiveness endpoints and additional analyses. Data from IDE subjects who do not provide consent for the study or subjects who previously exited the IDE will be censored at the time of IDE study exit in the endpoint analyses, but will not count toward the target enrollment sample size. All non-IDE subjects who undergo an implant procedure for the S-ICD System will be included in the endpoint analyses and will count toward the enrollment ceiling. All analyses may be done separately on IDE study subjects vs de novo implants. The statistical analyses related to this study will be executed by the sponsor and/or business partners working on behalf of the sponsor.

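### The 360-day life-expectancy exclusion has no exemption for already-implanted IDE subjects, so those refused at re-consent are censored because death is expected, and Kaplan-Meier all-cause mortality is biased slightly downward

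*Combined protocol and SAP*

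**What the plan says.** - **Criterion.** Section 8.3.2 excludes subjects with "Remaining life expectancy of less than 360 days". The synopsis repeats this. Neither limits it to new implants or says when life expectancy is judged.
- **Scope.** Section 8 opens with "Subjects with a remaining life expectancy of at least 360 days who are eligible for implantation with an S-ICD System" and then adds the previously implanted IDE subjects after an OR. The sentence can be read with the life-expectancy condition covering both routes or only the first.
- **Enrollment.** Under section 9.1 an IDE participant "who is implanted with the S-ICD System is considered enrolled upon signing the informed consent form (ICF". All other subjects are enrolled after consent and an implant procedure.
- **Clock.** In section 7.2.9, for IDE subjects, "annual follow-up visit windows are calculated from the original S-ICD System implant date (day 0". The example given there has a last IDE visit at day 540, and "then the first S-ICD PAS annual follow-up visit should occur at 720 days post implant".
- **Analysis set.** Section 10 says that all IDE subjects "who underwent an implant attempt will contribute to the analyses of the safety and effectiveness endpoints and additional analyses". It continues: "Data from IDE subjects who do not provide consent for the study or subjects who previously exited the IDE will be censored" at IDE exit. Separate IDE and de novo analyses are allowed but not required.
- **Outcome and method.** All-cause mortality is an additional pre-specified safety analysis (6.6) with no performance goal. Section 10.7.3 names Kaplan-Meier for time-to-event analyses.
- **Withdrawal.** Worsening prognosis is not among the reasons listed in section 7.4.

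**The concern.** In the de novo cohort the criterion acts at time zero. It restricts who is studied but does not distort follow-up. In the IDE cohort the same words act at re-consent, perhaps one to three years after time zero, and select on how the subject has fared since implant. Both cohorts are then placed on one time axis.

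Kaplan-Meier assumes that a subject censored at a given time has the same prognosis as those who remain. Here a rule of the protocol ends observation because death within a year is expected. The deaths that follow are not counted, and the survivors who remain stand in for the people who left. The direction, downward, follows from the mechanism and needs no outside data.

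At stake is the credibility of a descriptive long-term mortality figure, above all for the IDE cohort. Sites have reason to enforce the criterion, since an eligibility violation is one of only three kinds of deviation in section 12.8.

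**Working it through.** The documents state no mortality rate, no count of affected subjects and no bias figure, so there is nothing to reproduce. The check compares 5-year Kaplan-Meier mortality with and without the censoring.

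**From the documents.** IDE study size 330 (section 3); enrollment target 1,616 (7.1). The pooled set is taken as 330 IDE + 1,286 de novo = 1,616.

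**Assumed, not in the documents.** Annual mortality m = 3%, 5% or 8%; re-consent, coinciding with IDE exit, at t = 1, 2 or 3 years; share f = 1%, 3% or 5% of IDE survivors at t with under 360 days to live; one-year mortality in that group q = 60%; all other IDE survivors re-consent.

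**Formulas.** Survival to re-consent is S(t) = (1 − m)^t. After t, the unaffected IDE subjects have annual mortality r = (m − f·q)/(1 − f), so that first-year IDE mortality after t is still m. With k = 5 − t:

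- IDE, full follow-up: S(t) × [f(1 − q)^k + (1 − f)(1 − r)^k]
- IDE, affected subjects censored at t: S(t) × (1 − r)^k
- Pooled: S(t) times the average survival after t, weighted by the numbers at risk just after t

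**Middle case (m = 5%, t = 2, f = 3%).**

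- S(2) = 0.95² = 0.9025, and r = (0.05 − 0.018)/0.97 = 0.0330.
- Over 3 years: (1 − r)³ = 0.9043; (1 − q)³ = 0.064; de novo 0.95³ = 0.8574.
- Affected subjects: 330 × 0.9025 × 0.03 = 8.9.
- IDE, full: 0.9025 × (0.03 × 0.064 + 0.97 × 0.9043) = 0.7933, so mortality is 20.7%.
- IDE, censored: 0.9025 × 0.9043 = 0.8161, so mortality is 18.4%. Difference **−2.3 points**.
- Pooled, full: (1,286 × 0.95⁵ + 330 × 0.7933)/1,616 = 0.7778, so mortality is 22.2%.
- Pooled, censored: at risk after t are 1,160.6 de novo and 288.9 IDE. 0.9025 × (1,160.6 × 0.8574 + 288.9 × 0.9043)/1,449.5 = 0.7822, so mortality is 21.8%. Difference **−0.44 points**.

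**Range over the assumptions.**

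| Case | Pooled, full → censored | IDE, full → censored |
|---|---|---|
| Smallest shift: m = 8%, t = 3, f = 1% | 34.05 → 33.94 (−0.11) | 33.88 → 33.34 (−0.54) |
| Middle: m = 5%, t = 2, f = 3% | 22.22 → 21.78 (−0.44) | 20.67 → 18.39 (−2.28) |
| Largest shift: m = 3%, t = 1, f = 5% | 12.82 → 11.95 (−0.87) | 7.73 → 3.00 (−4.73) |

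The largest case is a boundary. There f·q = 3% = m, so r = 0 and every later IDE death falls in the affected group. With f = 3% at the same m and t, the shifts are −0.52 pooled and −2.69 in the IDE cohort.

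**Fewer reachable IDE subjects.** If half of the IDE survivors cannot re-consent for reasons unrelated to prognosis (an assumption), with 1,286 de novo subjects as before, the middle-case pooled shift falls from −0.44 to −0.25 points. The IDE-cohort shift in points does not fall, because it depends on the share affected; the number affected halves to about 4.5.

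**The case against.** **Nobody is deleted.** A reader might infer that refused IDE subjects drop out of the pooled analysis. Section 10 does not allow that: every IDE subject with an implant attempt contributes, and those who do not continue are censored at IDE exit. Earlier deaths and person-time stay in. If refused subjects and all earlier IDE deaths were dropped, the same model would give a pooled shift of −0.70 to −3.58 points. Section 10 prevents that larger error, and what remains is informative censoring.

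**The timing is inferred.** Section 8.3.2 does not say when life expectancy is judged, and section 8 is ambiguous about the IDE route. Section 10 names non-consenters and earlier exits, not subjects refused for life expectancy. This stands as a caution. Still, consent is the point of enrollment for IDE subjects, the exclusion is unqualified, and a subject who never enters this study has no follow-up in it after IDE exit.

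**330 is a ceiling.** The IDE study included sites outside the US (section 3), whereas this study uses US sites (7.1), and some IDE subjects had already exited. Refused subjects do not count toward 1,616, so the pooled set lies between 1,616 and 1,946. Both facts make the pooled shift smaller.

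**Shock effectiveness.** A reader might infer that losing episodes in the sickest IDE subjects biases this endpoint. It is a proportion of episodes converted (10.7.4), so lost episodes matter only if they convert at a different rate. The documents give no evidence of that.

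**Handling may lie in unseen text.** Most of 10.7.8 is redacted and the body of Appendix D is not shown, so no claim is made about either. A sensitivity analysis or the optional cohort split could reveal the lost follow-up but could not restore it.

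**Conclusion.** The point holds as a small downward bias in a descriptive outcome. Read as written, the exclusion reaches IDE subjects after implant, and those refused are censored because they are expected to die. Under the assumed inputs, 5-year all-cause mortality is understated by about 0.1-0.9 points pooled and 0.5-4.7 points in the IDE cohort. The upper ends come from a boundary case, and the pooled figure shrinks if fewer IDE subjects are reachable. The direction follows from the design; the size rests wholly on the assumptions.

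It does not reach the tested endpoints. Mortality has no performance goal. The primary safety endpoint counts a death only when a system component caused it, so Type I complications should be little affected. No bias in shock effectiveness is shown. This is worth correcting because it is cheap, not because a primary conclusion depends on it.

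**What to change.** 1. In 8.3.2 and the synopsis, state that remaining life expectancy is judged at the initial S-ICD implant procedure and that the criterion is not applied to IDE G090013 subjects already implanted. Reword section 8 so that the condition clearly attaches to the de novo route only.
2. Make separate reporting of all-cause mortality for IDE and de novo subjects mandatory; section 10 now leaves it optional.
3. Report how many IDE subjects did not enter this study, with the reason for each.

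**Cost.** A one-line amendment and one additional table. The registry follows standard of care, so no treatment is added. A few IDE subjects will contribute only short follow-up. Some gravely ill subjects may still decline consent and be censored at IDE exit, so the bias is reduced but not eliminated; items 2 and 3 let a reader judge what is left.
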